6.2 Randomization

The randomization sequence will be obtained by computer-generated random numbers and provided to each HVTN CRS through a Web-based randomization system. The randomization will be done in blocks to ensure balance across groups. At each institution, the pharmacist with primary responsibility for dispensing study products is charged with maintaining security of the treatment assignments (except in emergency situations as specified in the HVTN MOP). Randomization will be stratified by geographical region (Southern Africa and US).

6.3 Blinding

Participants and site staff (except for site pharmacists) will be blinded as to participant treatment group assignments. Study product assignments are accessible to those HVTN CRS pharmacists, DAIDS protocol pharmacists and contract monitors, and SDMC staff who are required to know this information in order to ensure proper trial conduct. Any discussion of study product assignment between pharmacy staff and any other HVTN CRS staff is prohibited. The HVTN SMB members also are unblinded to treatment assignment in order to conduct review of trial safety.

When a participant leaves the trial prior to study completion, the participant will be told he or she must wait until all participants are unblinded to learn his or her treatment assignment.

Emergency unblinding decisions will be made by the site investigator. If time permits, the HVTN 108 Protocol Safety Review Team (PSRT) should be consulted before emergency unblinding occurs.

6.4 Statistical analyses

This section describes the final study analyses, unblinded as to treatment group assignment. Data from enrolled participants will be analyzed according to the initial randomization assignment regardless of how many vaccinations they received. In the rare instance that a participant receives the wrong treatment at a specific vaccination time, the Statistical Analysis Plan (SAP) will address how to analyze the participant's safety data. Analyses are modified intent-to-treat analysis in that individuals who are randomized but not enrolled do not contribute data and hence are excluded. Because of blinding and the brief length of time between randomization and enrollment—typically no more than 4 working days—very few such individuals are expected.

Analyses for primary endpoints will be performed using SAS and R. All other descriptive and inferential statistical analyses will be performed using SAS, StatXact, or R statistical software.

No formal multiple comparison adjustments will be employed for multiple safety endpoints, multiple primary immunogenicity endpoints, or secondary endpoints. However, multiplicity adjustments will be made for certain immunogenicity assays specified in the SAP, when the assay is viewed as a collection of hypotheses (eg, testing multiple peptide pools to determine a positive response).

Data from HVTN 108 and 111 will be combined to assess the safety and immunogenicity of the MF59 regimens. Data from these studies may be evaluated with data from other phase 1/2a studies within the P5 partnership HIV vaccine program. Comparable eligibility criteria and validated assays for primary immunogenicity endpoints will be used to mitigate the potential bias introduced by combining data across studies conducted over an extended period of time.

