4.5 Trial design rationale

DNA, Protein, and the combination of the two, as well as the combination of each of these immunogens with other constructs have been widely evaluated. However, these investigations included a variety of different vaccine candidates in different combinations, doses, and with incongruent injection schedules. They were implemented in different populations and the immunological assessments were performed in a variety of different laboratories using different assays. HVTN 108, in the context of the suite of P5 trials, is in the unique position to compare the suggested regimens directly. Subsequently, the immunogenicity and safety profiles can also be compared unconditionally. In order to assess the impact of the different adjuvants in the respective doses on prime/boost versus simultaneous DNA/Protein injections, each individual combination is evaluated as its own regimen. This setup allows forming a rational decision on which regimen(s) warrant further evaluation in an efficacy trial. Furthermore, the overall number of participants will provide sufficient safety data to comfortably move into a phase 2b efficacy set up (see also Section 6.1).

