6.1 Accrual and sample size calculations

Recruitment will target enrolling 334 healthy, HIV-uninfected adult participants ages 18-40 in Southern Africa and the United States. Participants will be randomized to 8 treatment groups (7 vaccine groups and 1 placebo group). Vaccine groups 1-3 share the same DNA prime and test 3 different boosts consisting of DNA coadministered with a protein/adjuvant combination (gp120 proteins at 100 mcg with MF59 adjuvant, gp120 proteins at 100 mcg with AS01_B, or gp120 proteins at 20 mcg with AS01_B) at 2 timepoints. In groups 4-6 the DNA is coadministered with 1 of the protein/adjuvant combinations at 3 timepoints. An additional vaccine group (group 7) will test the proteins alone at the 20 mcg dose adjuvanted with $AS01_{B}$ administered at 3 timepoints. Groups 2, 3 and 5-7 will enroll 50 participants per group. Groups 1 and 4 evaluating the proteins adjuvanted with MF59 will enroll 30 participants per group as these two vaccine regimens are also being evaluated in HVTN 111 at sites in Southern Africa (HVTN 111, n=30 per group). Evaluation of these 2 regimens will pool data from HVTN 108 and HVTN 111 for a total of 60 participants per group. The primary purpose of the placebo group (Group 8 n=24) is to ensure blinding. To ensure that both men and women will be adequately represented in the trial, the trial will enroll at least approximately 40% of each sex overall. Hence, when approximately 200 participants of 1 sex are enrolled, recruitment of persons born of that sex will stop.

Since enrollment is concurrent with receiving the first study vaccination, all participants will provide some safety data. However, for immunogenicity analyses, it is possible that data may be missing for various reasons, such as participants terminating from the study early, problems in shipping specimens, low cell viability of processed peripheral blood mononuclear cells (PBMCs) or high background. Immunogenicity data from 17 phase 1 and 2 phase 2a HVTN vaccine trials, which began enrolling after June 2005 (data as of September 2014), indicate that 15% is a reasonable estimate for the rate of missing data at Month 6.5. For this reason, the sample size calculations in Section 6.1.2 for n=50 account for 7 enrolled participants on each group having missing data for the primary immunogenicity endpoint.

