6.4.3.1 Reactogenicity

The number and percentage of participants experiencing each type of reactogenicity sign or symptom will be tabulated by severity and treatment group and the percentages displayed graphically by group. For a given sign or symptom, each participant's reactogenicity will be counted once under the maximum severity for all injection visits. In addition, to the individual types of events, the maximum severity of local pain or tenderness, induration or erythema, and of systemic symptoms will be calculated. Kruskal-Wallis tests will be used to test for differences in severity between groups.

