6.4.4 Immunogenicity analysis

6.4.4.1 General approach

For the statistical analysis of immunogenicity endpoints, data from enrolled participants will be used according to the initial randomization assignment regardless of how many injections they received. Additional analyses may be performed, limited to participants who received all scheduled injections per protocol. Assay results that are unreliable, from specimens collected outside of the visit window, or from HIV-infected participants postinfection are excluded. Since the exact date of HIV infection is unknown, any assay data from blood draws 4 weeks prior to an infected participant's last seronegative sample and thereafter may be excluded. If an HIV-infected participant does not have a seronegative sample postenrollment, then all data from that participant may be excluded from the analysis.

For each of the 11 primary endpoints listed in Table 6-3, response rates will be analyzed by tabulating the frequency of positive response for each endpoint and treatment group at each timepoint for which an assessment is performed. For CD4+ and CD8+ T-cell response, response rates to the individual peptide pools will also be calculated. Crude response rates will be presented with their corresponding 95% confidence interval estimate calculated using the score test method [73]. For secondary and exploratory assay endpoints, response rates and 95% confidence intervals will be calculated if appropriate for the endpoint. Criteria for a positive response for an assay will be described in the SAP.

All of the primary assays, and likely some of the secondary assays, will have quantitative assay data, including IgG binding antibody magnitude, neutralizing antibody titers, area under the magnitude-breadth curve [AUC-MB] for the neutralizing antibody assay, and percentage of positive cells from the ICS assay. Quantitative data will be displayed as graphical and tabular summaries of the distributions by antigen, treatment group, and timepoint. For all primary and secondary immunogenicity endpoints, box plots and plots of estimated reverse cumulative distribution curves will be presented by group.

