Formal statistical comparisons between individual arms is not the primary objective of the trial, although these are likely to be made to better understand the effect of adjuvants on immune response and the effect of dose for arms adjuvanted with AS01_B. For comparisons in which the response rate for 1 of the groups is low (eg, $\leq 20\%$ for the class), statistical testing will use Fisher's exact test comparing the 2 response rates as most of the continuous data readouts would be left censored at the lower limit of detection. For comparisons in which the response rates for both groups are high (eg, $\geq 75\%$), the difference between groups will be tested using the continuous readouts with a nonparametric Wilcoxon rank sum test if the data are not normally distributed and with a 2-sample t-test if the data appear to be normally distributed.

HVTN 108, Version 2.0 / August 8, 2016

Some immunologic assays have underlying continuous or count-type readout that are dichotomized into responder/nonresponder categories (eg, CD4+ T cell response). If treatment group differences for these assays are best summarized by a mixture model of response rates and magnitudes, then Lachenbruch's test statistic [74] will be used to evaluate the composite null hypothesis of equal response rates in the 2 groups and equal response distributions among responders in the 2 such groups. This test statistic equals the square of a binomial Z-statistic for comparing the response rates plus the square of a Wilcoxon statistic for comparing the response distributions in the subgroup of responders. A permutation procedure is used to obtain a 2-sided p-value. For estimation, differences in response rates between groups will be estimated using the methods described above, and in the subgroup of positive responders, differences in location parameters between groups will be estimated using the methods described above.

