Based upon previous HVTN trials, missing 15% of immunogenicity results for a specific assay is common due to study participants terminating from the study early, problems in shipping specimens, or low cell viability of processed PBMCs. To achieve unbiased statistical estimation and inferences with standard methods applied in a complete-case manner (only including participants with observed data in the analysis), missing data need to be missing completely at random (MCAR). Following the most commonly used definition, MCAR assumes that the probability of an observation being missing does not depend on any participant characteristics (observed or unobserved). When missing data are minimal (specifically, if no more than 20% of participants are missing any values), then standard complete-case methods will be used, because violations of the MCAR assumption will have little impact on the estimates.

If a substantial amount of immunogenicity data are missing (at least 1 value missing from more than 20% of participants), then using the methods that require the MCAR assumption may give misleading results. In this situation, analyses of the immunogenicity endpoints at a specific timepoint will be performed using parametric generalized linear models fit by maximum likelihood. These methods provide unbiased estimation and inferences under the parametric modeling assumptions and the assumption that the missing data are missing at random (MAR). MAR assumes that the probability of an observation being missing may depend upon the observed responses and upon observed covariates, but not upon any unobserved factors. Generalized linear models for response rates will use a binomial error distribution and for quantitative endpoints, a normal error distribution. For assessing repeated immunogenicity measurement, linear mixed effects models will be used. If the immunological outcomes are left- and/or right- censored, then the linear mixed effects models of Hughes [75] will be used, because they accommodate the censoring. In addition, secondary analyses of repeated immunogenicity measurements may be done using weighted GEE [76] methods, which are valid under MAR. All of the models described above will include as covariates all available baseline predictors of the missing outcomes.

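### Between-group tests involving the MF59 groups name no dataset (HVTN 108 alone or pooled with HVTN 111) and no region term; if pooled, MF59 v AS01B is only partly randomised

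*Combined protocol and SAP*

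**What the plan says.** Section 6.1 plans 30 participants in each MF59 group (Groups 1 and 4) and 50 in each AS01B group. The MF59 groups are smaller because HVTN 111 gives the same two regimens to 30 participants each at Southern African sites. HVTN 108 itself enrols in Southern Africa and the US, in a split that is not stated. Section 6.2 stratifies randomisation by these two regions.

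Section 6.4 says: "Data from HVTN 108 and 111 will be combined to assess the safety and immunogenicity of the MF59 regimens". Section 6.1.2 names the pooled dataset for the ATP assessment of Groups 1 and 4. No sentence says which dataset serves the between-group tests:

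- Section 6.4.3.1, reactogenicity: "Kruskal-Wallis tests will be used to test for differences in severity between groups".
- Section 6.4.4.1, immunogenicity: Fisher, Wilcoxon, t and Lachenbruch tests, introduced with "Formal statistical comparisons between individual arms is not the primary objective of the trial, although these are likely to be made", in order to understand adjuvant and dose effects.

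None of these tests has a region or study term. Two passages point towards HVTN 108 data only. Section 6.4.4.1 says that "data from enrolled participants will be used according to the initial randomization assignment regardless of how many injections they received", and Section 4.5 says that "each individual combination is evaluated as its own regimen". Neither excludes HVTN 111 data. Covariates appear only in the models used when more than 20% of participants have a missing value: "All of the models described above will include as covariates all available baseline predictors of the missing outcomes". Region and study are not named there.

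**The concern.** MF59 versus AS01B is one of the programme questions in Section 4.3. That section also says that meeting ATP is not enough to advance a regimen, so the secondary comparisons have a role in selection.

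If the tests use pooled data, half of each MF59 arm comes from another study, in one region only, and was not randomised against AS01B. A regional or study difference could then look like an adjuvant effect, or hide one. Section 6.4 recognises that combining studies can introduce bias. Its remedies are comparable eligibility criteria and validated assays for the primary immunogenicity endpoints. Neither balances region, and the assay remedy does not reach reactogenicity. Leaving the dataset open also allows it to be chosen after results are seen.

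**Working it through.** **Inputs from the protocol.** MF59: 30 (HVTN 108) + 30 (HVTN 111) = 60 per regimen. AS01B: 50 per group. Missing immunogenicity data: 15% (Section 6.1).

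**Not in the documents, so assumed.** The Southern African share s of HVTN 108 (30, 50, 75 or 90%), the regional shift and the study effect.

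**Step 1: the plan's own figure.** Evaluable pooled MF59: 60 x 0.85 = 51, as in Section 6.1.2. Evaluable AS01B: 50 - 7 = 43, also as stated. For HVTN 108 alone, MF59 has 30 x 0.85 = 25.5.

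**Step 2: regional imbalance from pooling.** The pooled MF59 share is (30s + 30)/60 = 0.5 + 0.5s. The excess over AS01B is 0.5(1-s), that is 35, 25, 12.5 and 5 points at the four shares. A regional shift of 0.5 SD then gives a spurious difference of 0.5(1-s) x 0.5 = 0.175, 0.125, 0.0625 and 0.025 SD.

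**Step 3: Wilcoxon error, nominal 5%, no adjuvant effect.** Simulation with unit-variance normal readouts, 51 v 43 evaluable, 20,000 runs per cell and a regional shift of 0.5 SD. The stratified test is van Elteren by region. Repeat runs agree within about 1 point.

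| s | Pooled, unstratified | with study effect +0.25 SD | with study effect -0.25 SD |
|---|---|---|---|
| 30% | 12.3% | 28% | 5.2% |
| 50% | 7.5% | 19% | 4.5% |
| 75% | 5.9% | 14% | 5.4% |
| 90% | 4.8% | 10% | 7.6% |

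The pooled region-stratified test gives 4.8-5.1% with no study effect, 6.7-8.7% with +0.25 SD, and 6.4/7.7/8.3/8.7% with -0.25 SD. Stratifying by region removes the regional part only. With the negative study effect it does worse than the unstratified test at every share. The HVTN 108-only stratified test stays at about 5% throughout.

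**Step 4: power for a true 0.6 SD adjuvant effect.**

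- Pooled, s = 50%, regional shift 0.5 SD: 59% or 90% unstratified, depending on the direction of the effect; 77% stratified.
- Pooled, no regional difference: 80% unstratified; 74/77/78/79% stratified at the four shares.
- HVTN 108 only, no regional difference: 63% unstratified; 62% stratified.
- HVTN 108 only, regional shift 0.5 SD: stratifying gains at most about 1 point.
- HVTN 108 only, regional shift 1 SD: unstratified error 2.8-4.0% and power 53-60%; stratified about 5% and 62%.

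**Step 5: the other tests, for illustration.**

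- Kruskal-Wallis on seven vaccine arms, with MF59 n=60 and AS01B n=50. The assumed none/mild/moderate/severe distribution is 15/35/35/15% in the US and 30/40/20/10% in Southern Africa. Pooled unstratified error is 12.2/7.4/4.9/4.9%; region-stratified error is 4.8-5.1%. These figures exclude placebo, although Section 6.4.3.1 does not exclude it.
- Fisher, with assumed response rates of 10% (US) and 30% (Southern Africa): 10.5% and 5.8% at s = 30% and 50%; Cochran-Mantel-Haenszel 4.8-5.0%. At higher shares Fisher error is below 5%, and the low-rate condition in Section 6.4.4.1 would usually not select this test.

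**Step 6: does the missing-data model cover this?** With 15% missing per assay and four assays, the share of participants with any missing value lies between 15% (complete overlap) and 1 - 0.85^4 = 48% (independence). The 20% trigger may or may not be met, and it does not apply to reactogenicity.

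**The case against.** The strongest reply is that every pooling sentence concerns the evaluation of a regimen, and none mentions comparison with AS01B. Section 6.4.4.1 speaks of comparisons between arms of this trial, and analysis follows randomisation assignment. HVTN 108-only is therefore a natural reading, and on it there is no confounding. The unstratified test is then slightly conservative, and stratifying changes little unless regions differ strongly. All of this stands. It does not settle the matter: HVTN 111 participants can also be analysed as assigned, and the sentence in Section 6.4 makes no exception for tests.

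It is also true that these comparisons are not the primary objective, and that the regional split and both effects are assumed. The separate HVTN 108 SAP is not part of the document and may name the dataset. The protocol leaves the final ATP criteria, wrong-treatment safety data, certain multiplicity adjustments and positivity criteria to that SAP, but does not expressly leave the dataset or region adjustment to it.

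For the omnibus Kruskal-Wallis test, an all-groups-equal null means little if saline placebo is included, so its error figures show the mechanism and no more.

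**Conclusion.** The gap is real and limited; I would grade it CONSIDER. The tests name neither a dataset for Groups 1 and 4 nor the stratification factor. If pooled data enter, MF59 v AS01B is partly non-randomised. Under an assumed 0.5 SD regional shift, Wilcoxon error is about 12/8/6/5% at s = 30/50/75/90%, so inflation is negligible at shares of 75% or more unless there is also a study effect. An assumed study effect of 0.25 SD in either direction leaves the pooled region-stratified test at about 6-9%.

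A reader might infer three stronger things that the documents do not support:

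- **That the plan commits itself to a confounded adjuvant comparison.** The HVTN 108-only reading is open and carries no such bias.
- **That the primary immunogenicity assessment is undermined.** ATP names its dataset and sets each regimen against fixed thresholds. Comparisons among AS01B groups use no HVTN 111 data.
- **That stratifying a pooled test by region makes it safe.** It leaves any study effect in place, and the documents describe no AS01B group in HVTN 111 from which to estimate one.

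**What to change.** In Sections 6.4, 6.4.3.1 and 6.4.4.1, or in the separate SAP, before unblinding:

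1. Name the dataset for every test involving Group 1 or Group 4.
2. For the pairwise adjuvant comparisons (Groups 1 v 2 and 4 v 5), report the randomised HVTN 108-only comparison stratified by region. Use van Elteren in place of Wilcoxon, Cochran-Mantel-Haenszel in place of Fisher, a region term in place of the plain t-test, and within-region permutation for Lachenbruch.
3. If a pooled comparison is also shown, stratify it by region, label it partly non-randomised, and state that a study effect remains.
4. Run the Kruskal-Wallis reactogenicity test on HVTN 108 data or with region strata.
5. Keep pooled data for ATP and for description.

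The cost is wording and a few table rows, with no new data. The HVTN 108-only comparison has about 62% power for 0.6 SD, against 74-80% pooled. If regions do not differ, stratifying costs about 1 point of power in HVTN 108-only data and 1-6 points in pooled data.

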6.4.1 Analysis variables

The analysis variables consist of baseline participant characteristics, safety, and immunogenicity for primary- and secondary-objective analyses.

6.4.2 Baseline comparability

Treatment groups will be compared for baseline participant characteristics using descriptive statistics.

6.4.3 Safety/tolerability analysis

Since enrollment is concurrent with receiving the first vaccination, all participants will have received at least 1 vaccination and therefore will provide some safety data.

6.4.3.1 Reactogenicity

The number and percentage of participants experiencing each type of reactogenicity sign or symptom will be tabulated by severity and treatment group and the percentages displayed graphically by group. For a given sign or symptom, each participant's reactogenicity will be counted once under the maximum severity for all injection visits. In addition, to the individual types of events, the maximum severity of local pain or tenderness, induration or erythema, and of systemic symptoms will be calculated. Kruskal-Wallis tests will be used to test for differences in severity between groups.

